3.2.3. Exploratory Endpoints

The exploratory endpoints of the placebo-controlled period are as follows:

- Change from baseline in COAs, including
 - RWS with and without weights at Week 4, Week 12, Week 24, Week 36, and Week 48
 - Classic and FSHD TUG at Week 4, Week 12, Week 24, Week 36, and Week 48
 - Muscle strength by hand-held dynamometry at Week 4, Week 12, Week 24, Week 36, and Week 48
 - MFM Domain 1 at Week 12, Week 24, Week 36, and Week 48
 - FSHD-HI at Week 4, Week 12, Week 24, Week 36, and Week 48
 - PGIC at Week 4, Week 12, Week 16, Week 24, Week 36, and Week 48
- Change from baseline in inflammatory, immune, apoptotic, and muscle disease transcripts may be conducted in muscle biopsy at Week 16 or Week 36 and in circulating proteins in plasma and serum at Week 4, Week 12, Week 16, Week 24, Week 36, and Week 48.

3.3. Treatments

Study drug tablets in the placebo-controlled treatment period (losmapimod or placebo) and the open-label extension (losmapimod) will be dispensed to subjects at the visits detailed in Table 13-1 and Table 13-2 of the protocol, respectively.

During the placebo-controlled treatment period, subjects will receive either 15 mg losmapimod BID or placebo BID. In the open-label extension, all subjects will receive 15 mg losmapimod BID. As 7.5 mg losmapimod tablets will be used in this study, subjects will be taking 2 tablets, PO BID. The study drug should be taken with food, with the date and time of each dose taken recorded in the subject's diary.

4. General Statistical Considerations

4.1. Reporting Conventions

All data summaries, unless otherwise noted, will be presented by treatment group:

- Losmapimod 15 mg BID
- Placebo BID

The following conventions will be used for all the data presentations and analyses unless otherwise specified.

Appropriate descriptive statistics will be computed and displayed for both continuous and categorical variables. For continuous and quantitative variables, summaries will include n (number of subjects with non-missing data), mean, standard deviation (SD), Q1 (first quartile), Q3 (third quartile), median, minimum and maximum. Reporting conventions for descriptive statistics will follow the [REDACTED] Standard TLF Guidelines. For categorical variables, summaries will include the number and percentage of subjects who are in a particular category. Percentages will be computed based on the number of non-missing data points for patients in the applicable analysis set. Reporting of percentages will follow the [REDACTED] standard TLF Guidelines.

A total column will be presented for all demographic, baseline characteristic, baseline disease characteristic, protocol deviation, and prior and concomitant medication summaries.

All data will be listed by treatment group, FSHD repeat number category, subject ID, Ricci score, sex and visit date, if available. Any repeat assessments or additional assessments, along with any unscheduled visits, will be presented in the listings. Sort order of data listings will be treatment group, FSHD repeat number category, subject ID, and visit date, if available.

Statistical tests will be 2-sided and will be conducted at the significance level provided in [Table 12-1](#)), unless otherwise specified. P-values will be reported to 4 decimal places, with p-values less than 0.0001 reported as “<0.0001”.

All analyses will be performed using Statistical Analysis Software (SAS®, release 9.4 or higher). A separate document as an appendix to this SAP will contain the tables, listings, and figure (shells).

4.2. Handling of Missing Data

Missing data for primary efficacy endpoint will be handled as specified in the sensitivity analyses [Section 8.2.1](#).

All missing and partial dates for the prior/concomitant medications and adverse events will be handled as outlined in [Sections 7.1](#) and [9.1](#), respectively.

In categorical summaries, a missing category will be included if and only if any data for the given endpoint is missing.

Missing values for other individual data points will remain as missing, unless otherwise, stated.

4.3. Baseline, Study Day, and Change from Baseline Definitions

Unless indicated otherwise, baseline will be defined as the last non-missing evaluation on or before the day of first dose of study drug. In the event that the last non-missing evaluation and the study drug administration happen on the same day, timing of the evaluation will be used to determine the pre- or post-dose. If timing is not available, the evaluation is considered pre- or post-dose based on the schedule of events for that assessment. For example, AEs and concomitant medication are considered post-baseline evaluations.

For muscle biopsies, any assessment taken on the first day of study drug exposure will be considered baseline, irrespective of timing to study drug.

Relative study days will be calculated as:

$(\text{assessment date} - \text{dose administration date}) + 1$

if the assessment date is on the same day or after the dosing date, otherwise:

$(\text{assessment date} - \text{dose administration date})$.

Study day will be presented on all listings where appropriate.

Change from baseline will be computed as (post-baseline assessment value - baseline assessment value).

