1.3 Clinical Pharmacology

Elimination of losmapimod is almost exclusively by metabolism, with only 2% of the administered dose recovered as unchanged drug in urine and feces. The principal route of metabolism is via hydrolysis of the cyclopropylamide group to form a pharmacologically inactive metabolite, GSK198602. The predominant route of elimination of losmapimod, mostly as the GSK198602 metabolite, is via urine (approximately 65% of the dose), with approximately 29% of the dose eliminated via feces. The absolute oral bioavailability of the tablet formulation is 62%.

Following a single intravenous dose of losmapimod, the steady-state volume of distribution indicated extensive tissue distribution. After single-dose oral administration of 1 to 60 mg losmapimod, the maximum plasma concentration (C_{max}) and area under the plasma concentration-time curve extrapolated to infinity (AUC_{0-inf}) of losmapimod increased in an approximately dose-proportional manner for doses up to 20 mg but increased less than proportionally from 20 mg to 60 mg, likely due to saturation of absorption. The terminal half-life was approximately 10 hours for losmapimod and approximately 12 hours for GSK198602. After single-dose oral administration of losmapimod, exposure (area under the plasma concentration-time curve [AUC]) was approximately 2-fold higher for GSK198602 than it was for its parent losmapimod. The time to maximum plasma concentration (T_{max}) of losmapimod was reached approximately 1 to 4 hours after dose administration, while the T_{max} of GSK198602 was approximately 3 to 4 hours after dose administration.

Steady-state plasma concentrations of losmapimod were achieved 2 to 3 days after the initiation of repeat dosing. Slight accumulation (up to approximately 30%, on average) for AUC and C_{max} after once or BID dosing was observed. Consistent with single-dose administration, exposure (AUC) was approximately 2-fold higher for the metabolite GSK198602 than it was for its parent losmapimod.

Fulcrum Therapeutics Losmapimod
 Protocol FIS-002-2019, Version 4.0 (COVID-19 Pandemic Emergency Amendment) 10 April 2020

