3.2 Rationale of Study Design

3.2.1 Rationale of Dose Selection

The placebo-controlled treatment period was designed to evaluate the efficacy of losmapimod for treatment of FSHD at its root cause and the safety of losmapimod over placebo in subjects with FSHD1 over 48 weeks. The OLE was designed to evaluate the safety, tolerability, and efficacy of long-term dosing of losmapimod in subjects with FSHD1. Losmapimod is being developed for the treatment of FSHD based on its robust nonclinical efficacy in inhibiting *DUX4* expression and *DUX4*-regulated downstream gene transcripts and reducing apoptosis across multiple FSHD cell lines at achievable clinical exposures with minimal impact on myotube differentiation. Based on clinical PK/PD studies (Barbour et al, 2013), it is predicted that the proposed human dose of losmapimod for FSHD clinical trials at 15 mg BID would provide drug concentrations in skeletal muscles sufficient to significantly inhibit p38 α/β and reduce aberrant expression of *DUX4*. The planned dose to be tested is 15 mg BID. Prior results indicate the excellent safety and tolerability of losmapimod for chronic administration in the clinic and include the convenience of oral administration.

Heat shock protein 27 (HSP27) is a phosphorylated substrate of p38 α/β that has been demonstrated to be a relevant target engagement marker of p38 inhibition. There is a clear relationship between losmapimod plasma concentrations and target engagement for p38 α/β MAPK, as measured by phosphorylated HSP27 (pHSP27). Pharmacokinetic/PD modeling indicates that the 15 mg PO BID dose should result in 40% to 70% pHSP27 reduction (Barbour et al, 2013; Cherian et al, 2011, and summarized in the IB). Losmapimod PK in humans has been well characterized, including at the exposure levels expected for the planned dose of 15 mg BID in the proposed studies. Pharmacokinetic/PD modeling has demonstrated that the inhibition of pHSP27 is directly related to the plasma concentration of losmapimod and that as the losmapimod concentration changes with time, the resulting change in pHSP27 occurs almost instantaneously (Barbour et al, 2013). Preclinical data show that this change in pHSP27 correlates with a significant reduction in *DUX4* levels and transcriptional activity.

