6.1 Efficacy Assessments

6.1.1 Skeletal Muscle Needle Biopsy

The choice of the muscle(s) to be biopsied in this study will be determined by the investigator, informed by skeletal muscle MRI during screening. The bilateral vastus lateralis, vastus medialis, lateral gastrocnemius, medial gastrocnemius, and tibialis anterior will be evaluated for eligibility by MRI using a central reader. Only those muscles that are STIR positive with the predetermined range of MFF will be eligible for biopsy. This information will be communicated to the sites that will select the muscle or muscles for biopsy. Sites will select the best muscle(s) that meet the MRI criteria based on their own experience with muscle needle biopsy. The Week 16 or Week 36 muscle needle biopsies (for those subjects unable to have the Week 16 muscle biopsy due to the COVID-19 pandemic), will be performed in the same approximate muscle region as the pretreatment (Day 1) muscle biopsy.

The muscle tissue collected at each biopsy will be analyzed for DUX4 activity using a molecular panel of DUX4-regulated gene transcripts and for drug concentration and target

Fulcrum Therapeutics Losmapimod
Protocol FIS-002-2019, Version 4.0 (COVID-19 Pandemic Emergency Amendment) 10 April 2020
engagement by central laboratories. The tissue will be used to measure other gene transcripts and may be used to measure proteins related to the pathology of FSHD as part of exploratory biomarker endpoints.

The specific details of the biopsy procedures, materials to be provided, materials to be resourced locally, personnel qualification, and methods for tissue collection, processing, and analysis will be specified in the study reference manual.

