6.3 Pharmacokinetic and Pharmacodynamic Assessments

6.3.1 Pharmacokinetic Assessments

During the placebo-controlled treatment period, blood samples will be collected to measure the plasma concentrations of losmapimod at Day 1 (baseline), Week 4, Week 16, and Week 36 at the following time points: immediately predose and 4 hours (\pm 30 minutes) after administration of the study dose. Blood samples will also be taken, when feasible, after dosing during the Week 12, Week 24, and Week 48 visits, preferably \geq 1 hour after dosing ([Table 13-1](#)). During the OLE, blood samples will be collected to measure the plasma concentration of losmapimod after dosing at each visit, preferably \geq 1 hour after dosing ([Table 13-2](#)).

For each plasma PK sample, approximately 3 mL of blood will be collected via an intravenous catheter placed in an antecubital vein in the arm into a 3 mL, lavender-capped vacutainer tube containing K2-EDTA. The indwelling catheter will be kept patent by saline flush after each blood sampling. The exact actual clock time of withdrawal of the blood sample will be recorded.

Skeletal muscle biopsies will be taken at Day 1 (baseline; predose) and at Week 16 or Week 36 to assess the losmapimod concentrations in muscle during the placebo-controlled

Fulcrum Therapeutics Losmapimod
 Protocol FIS-002-2019, Version 4.0 (COVID-19 Pandemic Emergency Amendment) 10 April 2020
 treatment period ([Table 13-1](#)). Skeletal muscle biopsy procedures are described in [Section 6.1.1](#).

Further detailed handling, processing, storage, and shipping procedures for plasma and skeletal muscle biopsy PK samples are described in laboratory manuals.

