6.3.2 Pharmacodynamic Assessments

During the placebo-controlled treatment period, samples for assessing the target engagement estimates of losmapimod in peripheral blood will be collected at Day 1 (baseline) and Week 16 or Week 36 if it was not possible to collect the sample due to the COVID-19 pandemic, at the following time points: immediately predose and 4 hours (± 30 minutes) after taking the study dose ([Table 13-1](#)).

For drug target engagement measurements in skeletal muscle tissue during the placebo-controlled treatment period, each biopsy will be analyzed for pHSP27/total HSP27. Target engagement estimates of losmapimod in skeletal muscle biopsy will be taken at Day 1 (baseline; predose) and at Week 16 or Week 36 ([Table 13-1](#)). Skeletal muscle biopsy procedures are described in [Section 6.1.1](#). Target engagement in muscle will be compared to target engagement in blood collected on the same day.

Further detailed handling, processing, storage, and shipping procedures for target engagement samples are described in a laboratory manual.

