- ^t The choice of the muscle(s) to be biopsied in this study will be determined by the investigator, informed by skeletal muscle MRI during screening. The bilateral vastus lateralis, vastus medialis, lateral gastrocnemius, medial gastrocnemius, and tibialis anterior will be evaluated for eligibility by

Fulcrum Therapeutics

Protocol FIS-002-2019, Version 4.0 (COVID-19 Pandemic Emergency Amendment)

Losmapimod

10 April 2020

MRI using a central reader. Only those muscles that are STIR positive with the predetermined range of muscle fat fraction will be eligible for biopsy. The 12 patients who rolled over at Week 24 will not undergo the Week 36 muscle biopsy.

- u Blood samples for PK will be collected at Day 1 (baseline), Week 4, Week 16, and Week 36 at the following time points: immediately predose and 4 hours (± 30 minutes) after administration of the study dose. Blood samples will also be taken, when feasible, after dosing during the Week 12, Week 24, and Week 48 visits, preferably ≥ 1 hour after dosing.
- v Blood samples for target engagement will be collected on Day 1 (baseline), and Week 16 or Week 36, at the following time points: immediately predose and 4 hours (± 30 minutes) after administration of the study dose.

- x The appropriate amount of study drug supply (losmapimod or placebo) will be given to the subject at each applicable visit to allow for dosing until their next scheduled study visit plus additional tablets to cover the visit window. Study drug (losmapimod or placebo) will be administered as 2 tablets taken twice daily and should be taken with food. Subject diaries may only be used for a portion of the placebo-controlled portion of the trial to record the date and time of each dose taken. This information may also be used to calculate compliance. Subjects will record the date and time of each dose of study drug taken (losmapimod or placebo) in the subject diary. Subjects may be provided additional study drug via courier service, as applicable.
- y Subjects who are rolling over into the OLE will be dispensed open label losmapimod at the time of the rollover visit. Subjects may be provided open label losmapimod via courier or shipping service, as applicable.
- z All medications taken within 28 days before screening through the safety follow-up visit will be recorded.
- aa Large window given to accommodate the COVID-19 pandemic.

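### SAP 4.3 accepts a post-dose Day 1 muscle biopsy as baseline, against the protocol's predose definition; for muscle target engagement this can bias the treatment difference toward no effect

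*SAP*

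**What the plan says.** SAP 4.3 starts with a general rule. When an evaluation and the first dose fall on the same day, "timing of the evaluation will be used to determine the pre- or post-dose"; if no time is recorded, the schedule of events decides. It then exempts one type of sample: "For muscle biopsies, any assessment taken on the first day of study drug exposure will be considered baseline, irrespective of timing to study drug".

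The protocol has no such exemption. Section 6.3.1, on muscle drug levels, reads "Skeletal muscle biopsies will be taken at Day 1 (baseline; predose". Section 6.3.2 reads "Target engagement estimates of losmapimod in skeletal muscle biopsy will be taken at Day 1 (baseline; predose". Section 6.1.1 places the later biopsy in the same approximate "muscle region as the pretreatment (Day 1) muscle biopsy".

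The first dose is given at the Day 1 visit, so a Day 1 biopsy can fall after it. The schedule footnote on blood samples reads "Blood samples for target engagement will be collected on Day 1 (baseline), and Week 16 or Week 36, at the following time points: immediately predose", followed by a draw 4 hours after the dose. The biopsy footnote in the same schedule does not state a time relative to dosing.

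**The concern.** For a biopsy known to be predose, the general rule and the exemption give the same answer. The exemption matters when a biopsy is timed after the dose, and there it reverses the general rule.

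The protocol's own pharmacology suggests why this matters for target engagement. Section 3.2.1 says that as the plasma level changes, "the resulting change in pHSP27 occurs almost instantaneously". Section 1.3 says the peak plasma level "was reached approximately 1 to 4 hours after dose administration". Section 1.2 reports rapid distribution to muscle in rodents. A losmapimod biopsy taken some hours after the first dose may therefore already show inhibition. A placebo biopsy cannot.

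Muscle target engagement is a secondary endpoint. Protocol 7.6.5 calls for ANCOVA least-squares means, treatment differences and p-values for target engagement in blood and muscle. Section 6 of the SAP addendum confirms ANCOVA for the target engagement parameters, and addendum 2.1 extends the PD set to all dosed subjects, so placebo is included. A baseline covariate that treatment has already moved in one arm biases that difference. None of the sensitivity analyses in SAP 8.2.1 flags or excludes post-dose Day 1 biopsies.

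**Working it through.** The plan gives no figure on this point to reproduce. The check has two steps.

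**1. Could a post-dose Day 1 biopsy already be inhibited?**

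- Expected steady-state peak at 15 mg BID: 75 ng/mL (protocol 3.2.1).
- Accumulation: up to about 30% (protocol 1.3).
- Plasma level for robust engagement in muscle: above 30 ng/mL (protocol 3.2.1).
- Implied first-dose peak, taking the full 30%: 75 / 1.3 = about 58 ng/mL, which is above 30.

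So inhibition within hours of the first dose is plausible. It has not been measured in human muscle.

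**2. How large is the bias?**

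Work on the natural-log scale, as SAP section 11 does for blood; using it for muscle is an assumption. Let R be the true reduction, f the share of losmapimod baselines taken post-dose, and b the slope on baseline. Assume the Day 1 post-dose reduction also equals R.

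The losmapimod baseline mean shifts by f × ln(1 − R); the placebo mean shifts by 0. The treatment estimate becomes (1 − b·f) × ln(1 − R), so

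reported reduction = 1 − (1 − R)^(1 − b·f).

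Raw change without a covariate is the case b = 1. With baseline in the model, analysing the change or the post-baseline value gives the same treatment coefficient. Subtracting baseline therefore adds no second bias, and b is the fitted baseline slope.

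For R = 50%, a round value inside the protocol's predicted 40% to 70%:

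- f = 10%, b = 0.3: 1 − 0.5^0.97 = 48.9%. With b = 0.6: 1 − 0.5^0.94 = 47.9%.
- f = 25%, b = 0.3: 1 − 0.5^0.925 = 47.3%. With b = 0.6: 1 − 0.5^0.85 = 44.5%.
- Raw change (b = 1): 1 − 0.5^0.90 = 46.4% and 1 − 0.5^0.75 = 40.5%.

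A simulation covered the two ends of the predicted range, with 34 per arm, an assumed log-scale SD of 0.5, baseline/post-baseline correlation 0.3 to 0.6, and 1,500 runs per setting.

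| True reduction | Post-dose share f | Raw change (formula) | ANCOVA |
|---|---|---|---|
| 50% | 10% | 46% | 49% to 48% (formula) |
| 50% | 25% | 41% | 47% to 45% (formula) |
| 40% | 10% | 36.9% | 39.2% to 38.1% (simulated) |
| 40% | 25% | 31.8% | 37.9% to 35.5% (simulated) |
| 70% | 10% | 66.2% | 69.3% to 68.2% (simulated) |
| 70% | 25% | 59.5% | 68.2% to 66.5% (simulated) |

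At f = 0 the simulated ANCOVA returned 39.9% to 40.0% and 69.8% to 70.0%, so there is no bias without post-dose baselines. The simulated bias is somewhat smaller than the formula's. For R = 70% and f = 25% the formula gives 1 − 0.3^0.925 = 67.2% to 1 − 0.3^0.85 = 64.1%. The reason is that a mixture of pre- and post-dose baselines widens the baseline spread and flattens the fitted slope. The 50% rows are therefore, if anything, slightly pessimistic.

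**The case against.** The strongest case against has five parts.

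- **The harm is conditional.** The protocol requires a predose biopsy, and nothing says that a post-dose one occurred. If none did, the rule has no effect. This stands. A reader might infer from the wording of SAP 4.3 that post-dose biopsies had been taken; the documents do not show that.
- **Late biopsies would be visible.** SAP section 10 provides a listing of muscle sample collection times and sampling-time deviations. This stands in part: a listing shows the problem but does not change which value enters the ANCOVA.
- **The muscle comparison is thinly specified and carries little weight.** SAP section 11 and the PD-set summary tables name blood only, so the muscle analysis rests on protocol 7.6.5 and the addendum's general wording. Target engagement is outside the testing hierarchy of SAP 8.1, and a bias toward no effect does not favour losmapimod. This stands and limits the consequence.
- **The pharmacology is transported.** The near-instant response relates pHSP27 to plasma level, and the 40% to 70% is a modelled prediction. Full inhibition in muscle on Day 1 is an upper-bound assumption. This stands.
- **The exemption may be sensible for DUX4.** Protocol 3.2.2 calls the DUX4-regulated transcripts stably expressed, and a lenient rule keeps subjects in the primary analysis. This stands, and it is a reason to keep the exemption there.

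None of this removes the conflict with protocol 6.3.1 and 6.3.2.

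**Conclusion.** The point holds for muscle target engagement. The SAP's baseline rule contradicts the protocol and, for this endpoint, allows an on-treatment value to serve as baseline in the losmapimod arm only. The bias is toward no effect and modest: a true 50% reduction reported as about 49% to 48% at f = 10%, or 47% to 45% at f = 25%. This rests on three assumptions: the post-dose share f, which the documents do not give; Day 1 inhibition equal to on-treatment inhibition; and a baseline slope of 0.3 to 0.6.

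Three stronger readings are tempting but not supported:

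- **The larger raw-change losses** (50% reported as 46% or 41%). These apply only without the baseline covariate. On the log scale they overstate the ANCOVA bias by a factor of 1/b, that is 1/0.6 = 1.7 to 1/0.3 = 3.3.
- **Bias in the muscle drug-concentration endpoint.** That endpoint is the concentration at Week 16 or Week 36, summarized descriptively by time point. Day 1 does not enter it; only the Day 1 summary row would be affected.
- **Bias in the primary DUX4 endpoint.** The same rule sets the DUX4 baseline, but the documents give no evidence that the transcripts change within hours of a first dose. No such bias is claimed.

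**What to change.** Revise SAP 4.3 as follows.

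1. Limit the exemption from dose timing to DUX4.
2. For muscle pHSP27, and for the Day 1 row of the muscle concentration summary, apply the general timing rule of 4.3. Only predose biopsies count as baseline, and post-dose Day 1 values are set to missing.
3. State how an untimed Day 1 biopsy is classed. The general rule falls back on the schedule of events, whose biopsy footnote is silent on this, so the SAP should refer to protocol 6.3.1 and 6.3.2.
4. Report the number of post-dose Day 1 biopsies by arm.
5. Optionally, add a DUX4 sensitivity analysis that excludes those subjects and leave the primary analysis unchanged.

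The drafting cost is small: a short change to the SAP text, one count by arm and, if wanted, one extra table. The analytic cost is that subjects biopsied post-dose, in either arm, lose their muscle target-engagement baseline. With 80 enrolled, a 25% share in both arms would mean 0.25 × 80 = 20 lost baselines and a 10% share 8. If no biopsy was post-dose, nothing is lost and the count settles the question.
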